8.4. Multiple Comparisons and Multiplicity

Treatment comparisons will begin with the primary endpoint. If the resulting two-sided p-value is less than 0.05, then the next comparison of the secondary endpoint will be made, in the order of clinical importance, as outlined below.

- Change from baseline in average AM and PM subject-reported 12-hour instantaneous Total Nasal Symptom Score (iTNS) over the 14-day treatment period.
- Change from baseline in the overall Pediatric Rhinoconjunctivitis Quality of Life Questionnaire (PRQLQ) score on Day 15 (Visit 4) between treatment groups.
- Change from baseline in average AM and PM subject-reported 12-hour reflective Total Ocular Symptom Score (rTOSS) over the 14-day treatment period.

The testing procedure will continue until either all comparisons of interest are made, or until the point at which the resulting two-sided p-value is greater than 0.05. Once one of the tests is not significant, the testing will no longer be performed for the remainder of the endpoints.

Note: p-values for all treatment comparisons will still be displayed in the outputs of interest. The hierarchical testing will be applied when interpreting the analysis in the CSR.

No multiplicity adjustments will be made.

8.5. Analysis of the Primary Efficacy Endpoint

8.5.1. Primary Efficacy Analysis

The primary endpoint, change from baseline in average AM and PM subject-reported 12-hour rTNSS over a 14-day treatment period, will be evaluated using a mixed-effect repeated measures (MMRM) model. The model will adjust for study treatment, site, baseline 12-hour rTNSS and study day as the within-subject effect, with the assumption that any missing data is missing at random (MAR).

The interactions of site-by-treatment and baseline-by-treatment will be investigated separately using two independent models and will only be included in the final model if they are statistically significant at the alpha=5% level. In order to determine the interaction/s to be included in the final model, the following model-fitting process will be followed:

1. The main-effects model containing study treatment, site, baseline 12-hour rTNSS and study day will be fitted first:
 - a. Unstructured covariance will initially be assumed.
 - b. If the model does not converge using the unstructured covariance structure, the autoregressive (order 1) AR(1) structure will be used.
 - c. If the AR(1) structure also does not converge, other covariance structures deemed appropriate to fit the data will be used.
2. Two independent models will be fitted using the covariance structure of the model that converged in step 1: one model containing the site-by-treatment interaction and the other model containing the baseline-by-treatment interaction. If the interaction term is significant, it will be included in the final model. If convergence is not obtained after adding both of the interaction terms (if both are significant), the more significant interaction term will be kept in the model. Any interaction term that make model not converge will not be added to the final model.

The statements of a SAS® PROC MIXED analysis would be (if the interactions of treatment*baseline and treatment*site are not statistically significant):

```
PROC MIXED;
CLASS subject treatment site day;
MODEL change = treatment site baseline day;
REPEATED day / SUBJECT = subject TYPE=UN;
LSMEANS treatment / CL DIFF E ;
ODS OUTPUT LSMEANS=lsmeans ;
ODS OUTPUT DIFFS=diffs ;
RUN ;
QUIT ;
```

The adjusted means for each treatment and the estimated treatment differences for the treatment comparisons will be presented together with 95% confidence intervals for the differences and p-

values for the treatment comparisons. The adjusted means and estimated treatment differences for the treatment comparisons will also be plotted, with corresponding 95% confidence intervals.

Descriptive statistics (number of subjects, mean, standard deviation, median, minimum and maximum) will be provided for baseline, post treatment and change from baseline by treatment group and day.

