The primary endpoint, change from baseline in average AM and PM subject-reported 12-hour rTNSS over a 14 day treatment period, will be evaluated using a repeated measures analysis of covariance (ANCOVA) model, adjusting for study drug group, site, and baseline 12-hour rTNSS (linear, continuous covariate - defined as the average of the last 8 consecutive AM and PM assessments during the last 4 days of the placebo run-in period (from Day -4 PM assessment to the AM assessment on the day of randomization) and study day as the within-subject effect. The interactions of site-by-treatment and baseline-by-treatment will be investigated separately and will only be included in final model if they are statistically significant at the 5% level. At least 6 out of 8 assessments (reading scores) should be available in order to calculate baseline score of 12 hour rTNSS (linear, continuous covariate). An unstructured covariance will be assumed. Least square means of the treatment differences and associated 95% confidence intervals and p-values will be presented. Additional details or any changes will be provided in the SAP.

The efficacy comparison of GSP 301 NS, administered as [REDACTED] with placebo NS over 14 days of study drug will be tested at 0.05 significance level.

The primary analysis will be based on the FAS and a supportive analysis will be based on the PPS. Analyses of the secondary and other endpoints will be performed using a similar method as described for the primary endpoint. Efficacy within pre-specified subgroups of clinical interest (eg, age, sex, race, and ethnicity) will be examined.

Detailed statistical analysis and methods will be provided in the SAP.

Pharmacokinetic Analyses: Not applicable.

Pharmacodynamic Analyses: Not applicable.

Biomarker Analyses: Not applicable.

Pharmacogenomic Analyses: Not applicable.

Safety Analyses:

Descriptive statistics will be used to summarize AEs, vital signs, physical examination, focused ENT data and a comparison of the incidence rate of AEs between study drug groups will be presented. Detailed statistical analysis and methods will be provided in the SAP.

Interim analyses: No interim analysis is planned.

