13.7.1. Analysis of the Primary Efficacy Endpoint

The change from baseline in average AM and PM subject-reported 12-hour rTNSS over a 14-day treatment period will be derived by calculating an average score for each subject, based on the post-dose AM and PM assessments over the 14-day treatment period.

The primary endpoint, change from baseline in average AM and PM subject-reported 12-hour rTNSS over a 14-day treatment period, will be evaluated using a repeated measures analysis of covariance (ANCOVA) model. The model will adjust for study drug, site, baseline 12-hour rTNSS (linear, continuous covariate - defined as the average of the last 8 consecutive AM and PM assessments during the last 4 days of the run-in period from the Day -4 PM assessment to the AM assessment on the day of randomization), study day as the within-subject effect. The interactions of site-by-treatment and baseline-by-treatment will be investigated separately and will only be included in final model if they are statistically significant at the 5% level. At least 6 out of 8 assessments (reading scores) should be available in order to calculate baseline score of 12 hour rTNSS (linear, continuous covariate. An unstructured covariance will be assumed. Least square means (LSMs) of the treatment differences and associated 95% CIs and p-values will be presented. Additional details or any changes will be provided in the SAP.

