- Change from baseline in average of the AM and PM subject-reported rTOSS and iT OSS for each day.

- Change from baseline in AM subject-reported rTOSS and iTOSS for each day.
- Change from baseline in PM subject-reported rTOSS and iTOSS for each day.

Non-nasal symptoms will be assessed in a similar manner to the ocular symptoms above.

Physician assessed Nasal Symptom Score (PNSS):

- Change from baseline in PNSS and physician assessed individual nasal symptoms at Day 15 (Visit 4).

Pediatric Rhinoconjunctivitis Quality of Life Questionnaire (PRQLQ):

- Change from baseline in individual domains of the PRQLQ at Day 15.

Safety Endpoints

- AEs and SAEs.
- Vital signs.
- Physical examinations.
- Focused ears, nose, and throat (ENT)/Eye examinations.

Statistical methods:

Analysis Sets:

The Full Analysis Set (FAS) will consist of all subjects who have been randomized and received at least 1 dose of investigational product (IP) and have at least 1 post-baseline primary efficacy assessment. This will be the primary analysis set for efficacy analyses.

The Per Protocol Set (PPS) will consist of the subset of the FAS who do not meet criteria for PPS exclusion.

The Safety Analysis Set (SAS) will consist of all subjects who took at least 1 dose of study medication following randomization and will be used for all safety analyses.

Efficacy Analyses

The primary endpoint, change from baseline in average AM and PM subject-reported 12-hour rTNSS over a 14-day treatment period, will be evaluated using a mixed-effect repeated measures analysis of covariance (ANCOVA) model. The model will adjust for study treatment, site, baseline 12-hour rTNSS (linear, continuous covariate - defined as the average of the last 8 consecutive AM and PM assessments during the last 4 days of the run-in period from the Day -4 PM assessment to the AM assessment on the day of randomization) and study day as the within-subject effect, and site-by-treatment and baseline-by-treatment interactions. An unstructured variance-covariance matrix will be assumed as a start. Least square means of the treatment differences and associated 95% confidence intervals (CIs) and p-values will be presented. The primary analysis will be based on the FAS and a supportive analysis will be based on the PPS.

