8.6.1. Analysis of Change from Baseline in iTNSS and rTOSS

The analysis of change from baseline in iTNSS and rTOSS will use both the FAS (primary) and the PPS (supportive).

Similar to the primary analysis for the primary endpoint in section 8.5.1 above, the secondary endpoints (iTNSS and rTOSS) will be evaluated using a MMRM model, adjusting for covariates that include treatment, site, baseline and study day as the within-subject effect. The interactions of site-by-treatment and baseline-by-treatment will be investigated separately in the model and will only be included in final model if they are statistically significant at the alpha=5% level. An unstructured (UN) covariance will be assumed. If the model does not converge using the unstructured covariance structure, the autoregressive (order 1) AR(1) structure will be used. If this also does not converge other covariance structures deemed appropriate to fit the data will be used. The SAS® code will be similar to the primary endpoint.

The adjusted means for each treatment and the estimated treatment differences for the treatment comparisons will be presented together with 95% confidence intervals for the differences and p-values for the treatment comparisons. The adjusted means and estimated treatment differences for the treatment comparisons will also be plotted, with corresponding 95% confidence intervals.

Descriptive statistics (number of subjects, mean, standard deviation, median, minimum and maximum) will be provided for baseline, post treatment and change from baseline by treatment group and day.

8.6.2. Analysis of Change from Baseline in the Overall PRQLQ on Day 15

The change from baseline in the overall PRQLQ at Day 15 (Visit 4) will be analyzed for the FAS using an ANCOVA model adjusting for study treatment, site, and baseline PRQLQ (linear, continuous covariate). The interactions of site-by-treatment and baseline PRQLQ-by-treatment group will be investigated separately in the ANCOVA model and will only be included in the final model if they are statistically significant at the alpha=5% level. Baseline is defined as the PRQLQ score at Day 1 (Visit 2). For subjects who withdrew early from the study the PRQLQ score at their discontinuation visit will be used, regardless of what actual study day this visit occurred on.

The statements of a SAS® PROC MIXED analysis would be:

```
proc mixed;
class treatment site;
model change = treatment site baseline;
lsmeans treatment / cl diff;

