	NS	NS	NS	NS	xxx.x	xxx.xx	(xxx.x, xxx.x)	x.XXX
GSP 301 NS vs. Placebo NS	xxx	xxx	xxx.x (xx.xx)	xxx.x (xx.xx)	xxx.x	xxx.xx	(xxx.x, xxx.x)	x.XXX

Source: Listing 16.2.6.3

Baseline score is derived as the mean of the last 8 consecutive reading scores including the AM assessment on the day of randomization. Day 1 is derived as the average of Day 1 PM and Day 2 AM assessments and so on for the rest of the treatment period.

n= number of subjects with data available LS = least squares; SE = standard error

Statistical Analysis model: Mixed-effect repeated measures model with change from baseline as the dependent variable, treatment group and site as fixed effects, baseline score as covariate and study day as the within-subject effect.

Program: xxxx.sas Executed: DDMMYY HH:MM

Page X of Y

Programming Notes:

1. *Repeat the analysis for Days 1 to 14, replacing "Overall 14-day treatment period" with "Day 1", "Day 2", as is appropriate*
2. *Based on the results of the independent modeling for interactions, add the following footnotes:*
 - a. *If only treatment*site interaction is significant, footnote: "Site by treatment interaction is included in the model for the Overall 14-day analysis".*
 - b. *If only baseline*treatment interaction is significant, footnote: "Baseline score by treatment interaction is included in the model for the Overall 14-day analysis".*
 - c. *If both interactions are significant, footnote: "Site by treatment and baseline score by treatment interactions are included in the model for the Overall 14-day analysis".*

Table 14.2.1.3 Summary of Average AM and PM rTNSS by Day (Per Protocol Set)

Source: Listing 16.2.6.3

Repeat Table 14.2.1.1 for per protocol set.

Table 14.2.1.4 Summary of Repeated Measures Analysis Results of Average AM and PM rTNSS over the 14-day Treatment Period (Per Protocol Set)

Source: Listing 16.2.6.3

Repeat Table 14.2.1.2 for per protocol set.

Table 14.2.1.5 Subgroup Analyses (Age Group): Summary of Average AM and PM rTNSS by Day (Full Analysis Set)

Age Group 6 - <9

Treatment Group	Day	Average AM and PM rTNSS by Day				Change from Baseline			
		n	Mean (SD)	Median	Min, Max	n	Mean (SD)	Median	Min, Max
Placebo NS (N = xxx)	Baseline	xx	xx.x (xx. x)	xx.x	(xx,xx)				
	1	xx	xx.x (xx. x)	xx.x	(xx,xx)	xx	xx.x (xx. x)	xx.x	(xx,xx)
	2	xx	xx.x (xx. x)	xx.x	(xx,xx)	xx	xx.x (xx. x)	xx.x	(xx,xx)
	3	xx	xx.x (xx. x)	xx.x	(xx,xx)	xx	xx.x (xx. x)	xx.x	(xx,xx)
	...								

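### A 5% interaction pretest chooses the final primary model, and the SAP synopsis includes both interactions outright; if site-by-treatment enters, the treatment difference may weight sites equally or be non-estimable

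*SAP*

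**What the plan says.** SAP 8.5.1 first fits a main-effects model with treatment, site, baseline and study day. Step 2 then fits two further models, one per interaction, and says of each term: "If the interaction term is significant, it will be included in the final model". The only stated way out is failure to converge: "Any interaction term that make model not converge will not be added to the final model". The PROC MIXED code is printed only for one case: "if the interactions of treatment*baseline and treatment*site are not statistically significant". No code or site weighting is given for a model that contains site-by-treatment.

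Protocol 13.7.1 has the same condition; the terms "will only be included in final model if they are statistically significant at the 5% level". The protocol synopsis agrees. The rule also covers the secondary endpoints: iTNSS and rTOSS in SAP 8.6.1, and the overall PRQLQ in SAP 8.6.2 ("The interactions of site-by-treatment and baseline PRQLQ-by-treatment group will be investigated separately in the ANCOVA model").

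The programming notes for SAP Tables 14.2.1.2 and 14.2.1.6 report whichever model results as the overall 14-day result and add only a footnote such as "Site by treatment interaction is included in the model for the Overall 14-day analysis". Table 14.2.2.3.2 does the same for the overall PRQLQ.

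The SAP synopsis differs. It lists the model terms as including "study day as the within-subject effect, and site-by-treatment and baseline-by-treatment interactions", with no condition. SAP section 10 reports no changes from the protocol.

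**The concern.** There are two separate problems.

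- **Contradiction.** The SAP synopsis puts both interactions in the primary model unconditionally. SAP 8.5.1, both protocol passages and SAP 8.6 make them conditional. A programmer working from the synopsis would fit a different primary model.
- **The target depends on a pretest.** Without the interaction, the model weights each site by its information. With it, and with default LSMEANS margins (an assumption, since no weighting is stated), the treatment difference is the plain average of site differences. A site with two children then counts as much as one with forty. If any site has children in one arm only, the averaged difference cannot be estimated. A model with an empty site-by-arm cell can still converge, so the non-convergence exit does not catch this. No pooling of small sites is stated.

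If there is no primary p-value, the fixed-order testing in SAP 8.4 cannot start. Baseline-by-treatment matters less, because LSMEANS evaluates the difference at the mean baseline by default.

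**Working it through.** **Inputs from the documents** (Protocol 13.1, SAP 4.3.1): difference 1.0, SD 3.0, two-sided 5%, 90% power, 382 evaluable, 15% drop-out, about 450 randomised. **Assumed, because not given:** 15, 25 or 40 sites; site-size CV 0 (equal expected sizes), 0.7 or 1.0; simple 1:1 randomisation.

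**1. Planned figure.** The normal approximation gives 2 × 3.0² × (1.96 + 1.2815)² / 1.0² = 18 × 10.507 = 189.1, so 190 per arm. The noncentral t gives 191 per arm, or 382 in total (power 0.901). Then 382 / 0.85 = 449.4, so 450. Both planned numbers reproduce.

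**2. How often a term enters by chance.** Each pretest has a 5% chance when there is no true interaction. The chance that at least one enters is 1 − 0.95² = 9.75% if the tests are independent. Simulation gave 4.8-5.3% for site-by-treatment alone.

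**3. Chance of a one-arm site at N=450.** With equal expected sizes the mean site size is m = 450/K. Treating arm counts as Poisson, the chance that a site has exactly one empty arm is p = 2e^(−m/2)(1 − e^(−m/2)), and the chance that at least one of K sites does is 1 − (1 − p)^K.

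- K=40: m = 11.25, p = 0.0072, result 25%.
- K=25: m = 18, p = 0.00025, result 0.6%.
- K=15: m = 30, result 0.0%.

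With gamma-distributed sizes, k = 1/CV² and p = 2(1 + m/2k)^(−k) − 2(1 + m/k)^(−k). At CV 0.7 this gives 25%, 68% and 98% for 15, 25 and 40 sites. The simulations agree: 23%/68%/98% at CV 0.7, and 59%/92%/almost 100% at CV 1.0.

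**4. Loss of precision if the term enters and is estimable.** With a and b children per arm at a site and n = a + b, the variance ratio of the equal-weight to the main-effects contrast is R = [Σ(1/a + 1/b)/K²] × Σ(ab/n). Power is Φ(3.2415/√R − 1.96), which is 90% at R = 1. A separate run at N=382 with 15 sites gave √R of 1.02 with equal sizes, so Φ(3.178 − 1.96) = 89%. At CV 0.8 it gave 1.41, so Φ(2.299 − 1.96) = 63%. Over 15, 25 and 40 sites, power was 85-89% with equal sizes and 55-72% at CV 0.7-1.0.

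**5. The whole rule.** Simulation used each child's 14-day mean change, modelled as treatment plus site. This approximates the overall MMRM contrast and ignores baseline. If the site-by-treatment F-test was significant, the equal-weight contrast was used and scored as no rejection when non-estimable. There were 20,000 trials per setting, or 10,000 with a true interaction.

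| N=450 | Equal sizes | Unequal sizes |
|---|---|---|
| Power loss, no true interaction | 0.0-1.2 points | 1.9-4.5 points (CV 0.7-1.0) |
| No primary estimate, no true interaction | 0-1.2% | 1.3-4.9% (CV 0.7-1.0) |
| Power loss, true site-effect SD 0.5 (trigger 9-14%) | 0-2.1 points | 5.6-8.5 points (CV 0.7) |
| Power loss, true site-effect SD 1.0 (trigger 30-51%) | 0.1-7.2 points | 15-27 points (CV 0.7) |

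At N=382 with no true interaction the losses are 0.1-2.3 points (equal) and 2.2-4.7 points (CV 0.7-1.0). Type I error was 4.7-5.4% under the rule and 4.8-5.3% under main effects (N=450; equal sizes and CV 0.7).

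**6. If the synopsis is followed.** Both terms are then always in the model. The chance of no estimate is the full one-arm-site probability in step 3, not about 5% of it.

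**The case against.** The rule is prespecified in both documents, with its threshold and fitting order, and it does not inflate type I error. That stands: this is not an error-rate problem.

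The larger losses depend on scoring a non-estimable contrast as no rejection. Step 1 already produces a main-effects estimate, and falling back to it removes most of the loss. In a rerun at CV 0.7 (15/25/40 sites), losses with no true interaction fell from 1.5/2.9/5.0 points to 0.3/0.0/0.1. At a true site-effect SD of 1.0 they fell from 14.5/26.5/26.3 to 5.5/1.7/0.1. This also stands as a reading of the numbers: at 25 to 40 sites the loss is nearly all from having no estimate. But the SAP states no such fallback, and at 15 sites the fallback still loses some power.

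The site assumptions may be unfavourable. Blocking within site is neither stated nor excluded. With blocks of 4 (assumed), the one-arm-site chance falls from 25% to about 1.5% for 40 equal sites, but stays near 90% for 40 sites at CV 0.7. A run at N=382 with site blocking and moderate imbalance (CV 0.4-0.5), keeping only trials with both arms at every site, lost 0.4-0.7 points with no true interaction and 2.8 points at a true site-effect SD of 1.0 (15 sites).

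The conditional powers in step 4 are scaled to 90% for main effects. On the N=450 scale the unequal-size range is roughly 60-76%. The 40-site values rest on few estimable trials: 418 at CV 0.7 and 38 at CV 1.0.

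Finally, no harm from baseline-by-treatment is shown. Its pretest goes because one fixed model is wanted, not because of a measured loss.

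**Conclusion.** The concern holds and should be fixed; confidence is medium because site numbers, sizes and blocking are not stated. Two points need no assumption about sites: the SAP synopsis contradicts SAP 8.5.1 and the protocol, and the SAP gives neither site weights nor an estimability rule for a model it may make primary. The numerical cost is conditional. With equal sites and no true interaction it is about a point of power or less at N=450. With uneven sites it is a few points on average. It becomes large only if effects truly differ between sites and a non-estimable contrast counts as failure. The equal-weighting consequence assumes SAS default margins.

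**What to change.** Make the main-effects model (treatment, site, baseline, study day) the single primary model.

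- Delete step 2 of SAP 8.5.1 and the interaction text that introduces it, and the matching rules in SAP 8.6.1, SAP 8.6.2, the protocol synopsis and Protocol 13.7.1.
- Remove both interactions from the SAP synopsis.
- Remove the interaction footnotes from Tables 14.2.1.2, 14.2.1.6 and 14.2.2.3.2.
- Add: *Site-by-treatment and baseline-by-treatment are examined in separate supportive models and do not alter the primary model.*
- Report both tests and the by-site estimates as descriptive or sensitivity results. For the supportive site model, state the site weights and how one-arm or very small sites are handled.

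Nothing here argues for adding a day-by-treatment term to the primary model. The cost is a small SAP rewording and a matching protocol clarification before database lock. No new data are needed, and both interactions are still reported.

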4.3. Sample Size Considerations

4.3.1. Sample Size Justifications

A total sample size of 450 randomized subjects (225 subjects per treatment group) has been selected for this study.

The primary goal of the analysis of the primary endpoint will be to assess the superiority of GSP 301 NS versus (vs) GSP 301 placebo NS.

A sample size of 382 evaluable subjects, allocated 1:1, will provide 90% power to detect a between-group mean difference (GSP 301 NS vs placebo NS) of 1.0 in the absolute change from baseline in average AM and PM subject-reported 12-hour rTNSS over a 14-day treatment period (assuming a two-sided alpha of 5%). A standard deviation of 3.0 in the change from baseline in 12-hour rTNSS over a 14-day treatment period has been assumed. Assuming a drop-out rate of 15%, a total of approximately 450 subjects are planned to be randomized (225 subjects in each treatment group). Depending on the actual drop-out rate, the sponsor may decide to randomize high or lower number of subjects in order to meet the required sample size of 382 evaluable subjects.

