6.7.3. Change from Baseline

Change from baseline in average AM and PM 12-hour rTNSS over a 14-day treatment period

- For mixed-effect model repeated measures (MMRM) model, this will be derived by calculating a mean score for each subject, based on the post-dose PM of the dosing day and AM assessment of next day for each day (ie Day 1 measurement = Average of the PM assessment on Day 1 and AM assessment of Day 2 and so on).
- For Analysis of Covariance (ANCOVA) model, the overall mean change from baseline over the 14 day period includes assessment from Day 1 PM assessment through Day 15 in the morning.

The same derivation method will be applied to endpoint change from baseline in average AM and PM 12-hour for iTNSS, rTOSS, iTNSS, rTNSS, iTNSS, individual reflective/instantaneous nasal/non-nasal symptom scores.

For all other endpoints, change from baseline is calculated as the difference between the post-baseline result and the baseline result.

Percent change is calculated as (change from baseline / baseline result * 100).

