8.7. Efficacy Analyses of Other Endpoints of Interest

The analysis on endpoints including nasal symptoms, non-nasal symptoms, individual domains of PRQLQ and PNSS will be based on the FAS. Outputs based on the PPS will be produced only on an as needed basis for these endpoints, depending on the results from the primary and secondary endpoints.

Similar methods as described for the primary endpoint above will be applied, for the other endpoints nasal symptoms, ocular symptoms and non-nasal symptoms as listed in Section 3.2.3. Similar to the primary analysis for the primary endpoint in section 8.5.1 above, these other endpoints (nasal symptoms, non-nasal symptoms and ocular symptoms) will be evaluated using a MMRM model, adjusting for covariates treatment, site, baseline and study day as the within-subject effect. The interaction term day-by-treatment will also be included in the MMRM model for the by-day analysis for rTNSS and iTNSS. The individual symptom analysis will be conducted by including a 'by individual symptom' statement to the proc mixed model. An unstructured (UN) covariance will be assumed. If the model does not converge using the UN covariance structure, the autoregressive-order 1 (AR(1)) structure will be used. If this also does not converge other covariance structures deemed appropriate to fit the data will be used. The SAS® code will be similar to the primary endpoint. If there is no convergence for the MMRM model with day-by-treatment term, ANCOVA model will be used to present the by-day estimates for rTNSS and iTNSS.

Similar to the analysis for the secondary endpoint in Section 8.6.2 above, the other endpoints overall PNSS and individual domains PNSS, PRQLQ will be evaluated using an analysis of covariance (ANCOVA) model adjusting for covariates that include treatment, site and baseline. The individual domain analysis will be conducted by including a 'by individual domain' statement to the proc mixed model.

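### The primary MMRM, and those for iTNSS and rTOSS, omit treatment-by-day, so the estimate is a covariance-weighted average of the daily effects that need not equal the 14-day average effect

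*SAP*

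**What the plan says.** Protocol 13.7.1 says the primary variable, change from baseline in rTNSS over 14 days, is "derived by calculating an average score for each subject" from the post-dose diary entries. SAP 4.3.1 sizes the trial on that average: a difference of 1.0, two-sided alpha 5%, 90% power and 382 evaluable subjects. It adds: "A standard deviation of 3.0 in the change from baseline in 12-hour rTNSS over a 14-day treatment period has been assumed".

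For the MMRM, SAP 6.7.3 uses 14 daily means (Day 1 is the Day 1 evening and Day 2 morning scores, and so on). The code in SAP 8.5.1 is "MODEL change = treatment site baseline day", with an unstructured covariance. The fallback reads: "If the model does not converge using the unstructured covariance structure, the autoregressive (order 1) AR(1) structure will be used". Only site-by-treatment and baseline-by-treatment may be added later. The footnote to the Table 14.2.1.2 shell lists the same terms: "treatment group and site as fixed effects, baseline score as covariate and study day as the within-subject effect". SAP 8.6.1 repeats the model for iTNSS and rTOSS, "adjusting for covariates that include treatment, site, baseline and study day as the within-subject effect".

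The SAP specifies treatment-by-day only for daily results. SAP 8.7 says: "The interaction term day-by-treatment will also be included in the MMRM model for the by-day analysis for rTNSS and iTNSS". The shells for the separate AM and PM scores carry a matching footnote. SAP 6.7.3 also defines a variable for ANCOVA in which "the overall mean change from baseline over the 14 day period includes assessment from Day 1 PM assessment through Day 15 in the morning", but SAP Table 4 lists only the MMRM for the primary endpoint.

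**The concern.** Without treatment-by-day the model has one treatment coefficient for all 14 days, and the treatment difference from LSMEANS is that coefficient. Its generalised-least-squares estimate gives more weight to days that carry more information under the fitted covariance. It does not average the days equally.

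This would not matter if the effect were the same every day, but the protocol gives no assurance of that. Protocol 4.2 describes a slow onset for intranasal corticosteroids, up to several days to full benefit, and potentially quick relief from antihistamines.

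If the effect changes over the two weeks, the primary estimate, confidence interval and p-value answer a differently weighted question from the named endpoint, while the 90% power refers to the equal-weight average. The weights are unknown until the covariance is estimated, so nobody can say in advance which days drive the result. The primary p-value opens the testing hierarchy, and two of the three secondary endpoints use the same model.

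**Working it through.** **1. The plan's own figure.** Inputs from SAP 4.3.1: difference 1.0, SD 3.0, two-sided alpha 0.05, power 90%, drop-out 15%. The normal approximation gives 2 x (1.960 + 1.282)^2 x 3.0^2 / 1.0^2 = 189.1, so 190 per arm. The noncentral t first reaches 90% at 191 per arm (90.1%), which is 382 in total. Then 382 / 0.85 = 449.4, so 450. The planned numbers are reproduced, and they belong to the equal-weight 14-day mean.

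**2. What the planned model estimates.** Let d be the vector of 14 daily treatment differences, S the 14 x 14 within-subject covariance, and 1 a vector of ones. With complete data the treatment coefficient targets

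- w'd, where w = S^-1 1 / (1' S^-1 1).

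All weights are 1/14 = 7.1% only if every row of S has the same sum, as under compound symmetry with equal variances. Neither an unstructured nor an AR(1) covariance ensures this. With missing days the weights also depend on the missingness pattern.

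**3. AR(1) fallback.** For correlation rho, Day 1 and Day 14 each get 1 / (2 + 12(1 - rho)), and each other day gets (1 - rho) times that.

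- rho 0.7: 1/5.6 = 18% for each end day, 5.4% for each other day
- rho 0.8: 1/4.4 = 23% and 4.5%
- rho 0.9: 1/3.2 = 31% and 3.1%

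**4. Unstructured covariance, illustration only.** The following are assumptions, because the documents give no values: correlation 0.5 + 0.5 x 0.7^lag; S scaled so that the 14-day mean has SD 3.0; 191 per arm; effect starting at 30-70% of its plateau with a half-time of 2-3 days; true 14-day average 1.0; variance changing linearly, early (half-time 2 days) or late (quadratic). Power is from the noncentral t on 380 df.

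| Day 14 / Day 1 variance | Target of planned model | Power |
|---|---|---|
| 0.7 | 1.01-1.09 | 92-95% |
| 1.0 | 0.94-0.98 | 87-90% |
| 1.5 | 0.74-0.94 | 72-88% |
| 2.0 | 0.59-0.91 | 57-88% |
| Equal weighting, any ratio | 1.00 | 90% |

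With a 70% start only, the targets are 0.98, 0.90-0.94 and 0.84-0.91 at ratios 1.0, 1.5 and 2.0, with power 87-90%. Under the AR(1) fallback the same onset profiles give 0.94-0.98, 0.92-0.98 and 0.88-0.96 at rho 0.7, 0.8 and 0.9. For an effect fading from 1.4 to 0.6, the same covariances give 1.13-1.14 at ratio 1.5 and 1.21-1.23 at 2.0, so the error can go either way. A flat effect gives exactly 1.0 throughout.

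**5. Simulation check.** 1,500 trials per scenario, unstructured maximum-likelihood fit, complete data, 191 per arm, no site or baseline terms (Monte Carlo error of a mean about 0.008):

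| Scenario | Planned model | With treatment-by-day |
|---|---|---|
| Equal variance, 50% start | 0.954, power 88% | 0.991, power 90% |
| 1.5x linear, 50% start | 0.870, power 83% | 0.999, power 89% |
| 2.0x linear, 30% start | 0.689, power 67% | 0.989, power 89% |

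With 225 per arm and 15% random drop-out, the first two scenarios give 0.960 and 0.846 for the planned model and 1.015 and 0.994 with the interaction. The mean of each subject's available days gives 0.993 and 0.971.

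**6. Null case.** If there is no effect on any day, w'd = 0 whatever the weights. In separate simulations under other covariances (1,000 runs each), the planned model rejected in 5.1-5.7%.

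**The case against.** The strongest reply is that the model is pre-specified and consistent. Protocol 13.7.1 describes a repeated-measures model with the same terms, the SAP follows it, and the SAP supersedes the protocol where they differ. A common-effect model is also the more efficient one if the effect really is constant. That is right: this is not a departure from the protocol. But the same protocol section derives the endpoint as a per-subject average, and consistency between documents does not make the model estimate it.

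The size of the problem is also assumed, not documented. With equal variances the loss is small, and the lowest figures need both a doubling of variance and a 30% starting effect. The SD of 3.0 may be cautious: the confidence intervals in Protocol 4.4 for the two earlier phase 3 trials, at about 295 per arm, imply about 2.5. Those trials were in adults and adolescents, and their model is not stated. At SD 2.5 the lowest powers become 86% (1.5x) and 73% (2.0x). These points limit the likely damage but do not change what is being estimated.

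Finally, the Table 14.2.1.2 shell asks for Day 1 to 14 estimates beside the overall one, so readers will see the daily profile. That helps interpretation but leaves the primary estimate and p-value as they are, and the daily estimates need not average to the overall figure beside them.

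**Conclusion.** The concern holds and should be fixed. That the planned models for rTNSS, iTNSS and rTOSS weight days by the inverse covariance is exact algebra, with high confidence. They match the 14-day average effect only under conditions the plan does not secure. The practical size is unknown: it could be nil or negligible, or it could be material if daily variance changes and the effect builds or fades. Every target other than 1.0 above depends on an assumed covariance and effect profile. The issue concerns the estimand, the reported effect and power; it is not a false-positive route.

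**What to change.** In SAP 8.5.1, state that the estimand is the equal-weight average of the 14 daily treatment differences. Add `treatment*day` to the MODEL statement for rTNSS, iTNSS and rTOSS. Keep the existing LSMEANS request for treatment, which then averages the days equally, or write an explicit contrast with 1/14 per day. Keep the likelihood-based missing-at-random handling, and use the same mean model under the AR(1) fallback. A baseline-by-day term and Kenward-Roger degrees of freedom are optional. ANCOVA of the 14-day mean should be at most supportive, because it is equivalent only with complete data.

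The cost is the added term, matching wording in SAP 8.5.1 (including the model-fitting steps), SAP 8.6.1 and the synopsis, and the footnotes of Table 14.2.1.2 and of the age-subgroup shell, Table 14.2.1.6. No covariance parameters are added and 382/450 stands. SAP 8.7 already allows for non-convergence of the day-by-treatment model, so the fallback for the primary analysis should be stated too. If the effect is truly constant, the standard error is about 1-5% larger for variance ratios 0.7-1.5, 6-12% larger at 2.0, and 4-5% larger if AR(1) holds. That larger standard error is the one the sample size was planned on.
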